4.2.2 Overall Survival at 24 months

Overall survival at 24 months is defined as probability of survival at 24 months based on Kaplan-Meier method. It will be estimated only when minimum follow-up is 24 months or more. In case the minimum follow-up is less than 24 months, but it is judged that data immaturity does not affect interpretability of the results, 24 months OS rate will be provided.

5 SAMPLE SIZE AND POWER

This is a Phase 3, randomized, open label, multicenter study of RT + nivolumab versus RT + TMZ in adult (≥ 18 years) subjects with newly diagnosed GBM subjects with unmethylated MGMT tumors.

Primary objective of the study is to compare the overall survival (OS) of RT+ nivolumab versus RT+TMZ in subjects with newly diagnosed GBM subjects with unmethylated MGMT tumors after surgery.

The sample size for this study is based on the following assumptions:

- 1) OS follows exponential distribution
- 2) Median OS in RT + TMZ arm is 13.0 months (Weller 2009⁵)
- 3) Hazard ratio (HR) of arm RT + nivolumab vs. RT + TMZ is 0.72, translated to median OS improvement of 5.0 months (13.0 months vs. 18.0 months for arm RT + TMZ and arm RT + nivolumab, respectively)

At least 390 events (i.e., death) provide 90% power to detect a hazard ration (HR) of 0.72 with an overall type 1 error of 0.05 (two-sided). This translates to an observed HR of 0.82 (median OS of 13.0 vs. 15.8 months) or less resulting in a statistically significant improvement.

Approximately 550 subjects will be randomized to the two arms (RT +nivolumab vs. RT + TMZ) in a 1:1 ratio stratified by complete or partial resection at baseline. Accrual will take approximately 10 months. The total duration of the study from start of randomization to final analysis of OS is expected to be approximately 33 months (10 months of accrual + 23 months of follow-up (Table 5-1)

Power calculations were done using East v 6.3.

Table 5-1: Key Parameters of Sample Size calculation

Assumptions	Analysis	Goal/Timing (from first subject randomized)	Significant Nominal p-value	Probability for declaring superiority Under HA/H0
$\alpha = 0.05$	Final	390	Superiority Observed nominal	90%/ 5%

Table 5-1: Key Parameters of Sample Size calculation

[figure not shown]

Assumptions	Analysis	Goal/Timing (from first subject randomized)	Significant Nominal p-value	Probability for declaring superiority Under HA/H0
Power = 90%	Superiority	OS events/ 33 months	p-value ≤ 0.05	
Control arm (RT+TMZ) median OS = 13.0 months;			No Superiority nominal p-value > 0.05	
Treatment arm (RT + Nivolumab) Median OS = 18.0 months HR = 0.72				

6 STUDY PERIODS, TREATMENT REGIMENS AND POPULATIONS FOR ANALYSES

6.1 Study Periods

- Baseline period:
 - Baseline evaluations or events will be defined as evaluations or events that occur before the date and time of the first dose of study treatment. Evaluations (laboratory tests, pulse oximetry and vital signs) on the same date and time of the first dose of study treatment will be considered as baseline evaluations.
 - In cases where the time (onset time of event or evaluation time and dosing time) is missing or not collected, the following definitions will apply:
 - ◆ Pre-treatment AEs will be defined as AEs with an onset date prior to but not including the day of the first dose of study treatment
 - ◆ Baseline evaluations (laboratory tests, pulse oximetry and vital signs) will be defined as evaluations with a date on or prior to the day of first dose of study treatment
 - If there are multiple valid assessments on or prior to the first dose of study treatment:
 - ◆ For laboratory tests, the latest non missing labs value on or before first dose date (and time if collected) will be used as the baseline in the analyses. For 'LIPASE' and 'GLUCOSE', for treated subjects only, the last predose assessment with non-missing toxicity grade will be considered as baseline. If multiple assessments exist with the same collection date (and time if collected) and entry date and time, then the first observation is used as baseline.

- 
- 
- 
- Post baseline period:
 - On-treatment AEs will be defined as AEs with an onset date and time on or after the date and time of the first dose of study treatment (or with an onset date on or after the day of first dose of study treatment if time is not collected or is missing). For subjects who are off study treatment, AEs will be included if event occurred within a safety window of 30 days (or 100 days depending on the analysis) after the last dose of study treatment. No “subtracting rule” will be applied when an AE occurs both pre-treatment and post-treatment with the same preferred term and grade.
 - On-treatment evaluations (laboratory tests, pulse oximetry and vital signs) will be defined as evaluations taken after the day (and time, if collected and not missing) of first dose of study treatment. For subjects who are off study treatment, evaluations should be within a safety window of 30 days (or 100 days depending on the analysis) after the last dose of study treatment.

6.2 Treatment Regimens

The treatment group “**as randomized**” will be retrieved from the IVRS system

- Arm RT+TMZ: Radiotherapy + Temozolomide
- Arm RT+N: Radiotherapy + Nivolumab

The treatment group “**as treated**” will be the same as the arm as randomized by IVRS. However, if a subject received the incorrect drug for **the entire period** of treatment, the subject’s treatment group will be defined as the incorrect drug the subject actually received.

Unless otherwise specified, the safety analysis will be based on the treatment group “as treated”.

Unless otherwise specified, the efficacy analysis will be based on the treatment group “as randomized”.

6.3 Populations for Analyses

- All Enrolled subjects: All subjects who signed an informed consent form and were registered into the IVRS.
- All Randomized subjects: All enrolled subjects who were randomized to any treatment arm.

- All Treated subjects: All randomized subjects who received at least one dose of study drug.
- TMB evaluable subjects: All randomized subjects who have a baseline TMB value.
- Response evaluable subjects: Randomized subjects with measurable lesions at baseline.

Unless otherwise specified, the safety analyses will include all treated subjects.

Unless otherwise specified, the efficacy analyses will include all randomized subjects.

7 STATISTICAL ANALYSES

7.1 General Methods

Unless otherwise noted, discrete variables will be tabulated by the frequency and proportion of subjects falling into each category, grouped by treatment. Percentages given in these tables will be rounded to the first decimal and, therefore, may not always sum to 100%. Percentages less than 0.1 will be indicated as '< 0.1'. Continuous variables will be summarized by treatment group using the mean, standard deviation, median, minimum, and maximum values.

Time-to-event variables (e.g. time-to resolution) will be analyzed using the Kaplan-Meier technique. When specified, the median will be reported along with 95% CI using Brookmeyer and Crowley method⁶ (using log-log transformation for constructing the confidence intervals⁷).

The conventions to be used for imputing missing and partial dates for analyses requiring dates are described in [Section 8](#).

7.1.1 Adverse Events, Serious Adverse Events, Multiple events, Select Adverse Events, Other Events of Special Interest and Immune-Mediated Adverse Events

Drug-related AEs are those events with relationship to study drug "Related", as recorded on the CRF. If the relationship to study drug is missing, the AE will be considered as drug-related.

Serious adverse events consist of AEs deemed serious by the Investigator and flagged accordingly in the CRF and clinical database.

Adverse events leading to study drug discontinuation are AEs with action taken regarding study drug(s) = "Drug was discontinued".

Adverse events leading to dose delay are AEs with action taken regarding study drug(s) = "Drug was delayed".

Adverse event that led to dose delay of the oral drug (similarly defined as dose omission or dose interruption) will be coded with action "Drug was interrupted".

Adverse events leading to dose reduction are AEs with action taken regarding study drug(s) = “Dose was reduced”.

Adverse events will be coded using the Medical Dictionary for Regulatory Activities (MedDRA), and the most recent version of the dictionary at the time of the database lock will be used. Adverse events results will be graded for severity using NCI Common Terminology Criteria for Adverse Events (CTCAE) and the most recent version of the criteria at the time of the database lock will be used.

In the AE summary tables, unless otherwise specified, subjects will be counted only once at the Preferred Term (PT), only once at the System Organ Class (SOC), and only once at subject level for the counting of total number of subjects with an AE. The AE tables will be sorted by the SOCs and then PTs. SOC will be ordered by descending frequency overall and then alphabetically. PTs will be ordered within SOC by descending frequency overall and then alphabetically. The sorting will be done based on the ‘Any Grade’ column of the experimental arm when arms are presented side-by-side.

Unless otherwise specified, the AE summary tables will be restricted to on-treatment events regardless of the causality.

Analyses that take into account the multiple occurrences of a given adverse event will be conducted (see [Section 7.6.9](#)). To prepare these analyses, the CRF data will be processed according to standard BMS algorithms⁸ in order to collapse adverse event records into unique records based on the preferred term. These data will be presented as the rate per 100 person-years of exposure. These analyses will take into account all on-treatment events (allowing more than 1 event per subject) and the total exposure time. The person-year exposure will be computed as the sum over the subjects’ exposure expressed in years where the exposure time is defined as

- $(\text{Date of last dose of study treatment} - \text{date of first dose of study treatment} + 31 \text{ days (or 101 days, depending on the analysis)}) / 365.25$, for subject who are off study treatment and were followed for at least 30 days (or 100 days, depending on the analysis) after last dose of study treatment.
- $(\text{Last known alive date} - \text{date of first dose of study treatment} + 1) / 365.25$, for subjects who are still on-treatment or who are off study treatment and were followed less than 30 days (or 100 days depending on the analysis) after last dose of study treatment.

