4.5 Selection and Timing of Dose for Each Subject

Dosing schedules for both arms are detailed in [Table 4.5-1](#). All subjects will undergo surgical resection and radiotherapy as outlined in [Sections 3.1](#). For the RT + nivolumab arm, the first dose of nivolumab is to be administered within 7 days of randomization. For the RT + TMZ arm, the first dose of temozolomide is to be administered at the beginning of radiotherapy. Treatment details

are described separately for each arm below; treatment modifications (eg, dose delay, reduction, or discontinuation) will be based on specific laboratory and AE criteria, as described in Sections 4.5.1 and 4.5.2.

Table 4.5-1: Selection and Timing of Dose

Drug	Dose	Frequency of administration	Route of administration	Duration
Arm RT + Nivolumab (BMS-936558)	240 mg, then 480 mg after 8 doses	Every 2 weeks, for 8 doses, then Every 4 weeks after 8 doses	30 minute intravenous (IV)	Until progression, unacceptable toxicity, or discontinuation from treatment
Arm RT + TMZ (Temozolomide)	75 mg/m ² daily during RT then 150 mg/m ² D1-5 for C1 and increased to 200 mg/m ² D1-5 for C2-C6 as tolerated	Daily from first day of RT to last day of RT (not to exceed 49 days) then 4 week break followed by TMZ daily for 5 days every 28 days x 6 cycles ^a	Oral (PO)	Until completion of dosing, progression, unacceptable toxicity or discontinuation from treatment

^a Additional cycles of temozolomide are permitted for subjects enrolled in Japan

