4.5.2 Temozolomide Dosing

4.5.2.1 Temozolomide Dose and Schedule

Subjects on RT + TMZ will be administered temozolomide (TMZ, Temodar[®]) daily during RT and as maintenance therapy for 6 cycles. TMZ dosing will be performed according to institutional standard; the following guidance is drawn from published literature.

Temozolomide (TMZ) will be dosed at 75 mg/m² once per day continuously throughout RT, typically for 42 days and with a maximum of 49 days. See [Table 4.5.2.3-1](#) for dose modifications during concomitant RT + TMZ dosing. After completion of RT, there will be a 4-week break. Subjects will receive 6 cycles of temozolomide daily x 5 days every 28 days.

Dose Level	TMZ Dose in mg/m²/day	Notes
-1	100 mg/m ² /day	Reduction for prior toxicity
0	150 mg/m ² /day	Dose during Cycle 1
1	200 mg/m ² /day	Dose during C2-6 in absence of TMZ-related toxicity

Source: adapted from Temodar[®] package insert (PI)

In the first maintenance cycle TMZ is given at a dose of 150 mg/m², and then increased to 200 mg/m² in cycle 2 as follows: If, during the first cycle, all non-hematologic AEs observed were grade ≤ 2 (except alopecia, nausea and vomiting) and with platelets ≥ 100 x 10⁹/L and ANC ≥ 1.5 x 10⁹/L, then the temozolomide dose should be escalated to dose level 1 and this dose should be used as the starting dose for subsequent cycles. Doses of TMZ are not precise but are adjusted based on tolerance; rounding of up to 10% is entirely acceptable.

If treatment after cycle 1 has to be delayed because of ongoing non-hematologic AEs of grade ≥ 2, then no escalation is possible. If the dose was not escalated at Cycle 2, then the dose should not be escalated in further cycles based on AEs (see [Table 4.5.2.3-2](#)). If there was a prior dose reduction during the concomitant period with RT, then dose -1 should be the starting dose for subsequent cycles. Table 4.5.2.1-1 describes dose levels during temozolomide monotherapy.

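### Crude on-treatment AE percentages cover unequal time in the two arms, and the overall person-year rate corrects for this only if the AE hazard is roughly constant

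*SAP*

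**What the plan says.** SAP Section 6.1 starts the on-treatment period at first dose. Once a subject has stopped dosing, the rule is: "AEs will be included if event occurred within a safety window of 30 days (or 100 days depending on the analysis"). That window is counted from the final dose. SAP Section 7.1.1 then states: "Unless otherwise specified, the AE summary tables will be restricted to on-treatment events regardless of the causality". It allows for arms shown side by side. It also plans an analysis of repeated events, which divides all on-treatment events by total exposure time: "These data will be presented as the rate per 100 person-years of exposure". The exposure time uses the same 30- or 100-day tail.

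Protocol Table 4.5-1 gives the treatment durations. For nivolumab: "Until progression, unacceptable toxicity, or discontinuation from treatment". For temozolomide: "Until completion of dosing, progression, unacceptable toxicity or discontinuation from treatment". The temozolomide schedule is daily dosing during radiotherapy, "typically for 42 days and with a maximum of 49 days" (Protocol Section 4.5.2.1), "then 4 week break followed by TMZ daily for 5 days every 28 days x 6" cycles (Table 4.5-1). A footnote adds: "Additional cycles of temozolomide are permitted for subjects enrolled in Japan". Protocol Section 3.1.3 moves a subject who completes six maintenance cycles into follow-up. Protocol Section 4.5.1.6 lets nivolumab continue past suspected progression until progression is confirmed.

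**The concern.** A subject still progression-free after about seven months leaves the AE window if on temozolomide but stays in it if on nivolumab. The incidence tables count events of any cause, so the nivolumab arm has longer to accrue events from the disease, steroids or late effects of radiotherapy as well as from the drug. A reader would naturally turn to the exposure-adjusted rate for a fair comparison. That rate is a single average over each arm's whole window, and the extra nivolumab time all comes late. If the hazard changes over time, the two averages describe different mixtures of early and late time.

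The safety half of the benefit-risk comparison is at stake. The overall survival analysis is not affected.

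**Working it through.** The documents give no expected exposure, median progression-free survival (PFS) or AE rate, so there is no figure of the plan's own to reproduce on this point.

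**Windows, from the documents**
- Last planned temozolomide dose: 42 + 28 + 5 × 28 + 5 = day 215. Coverage ends at 215 + 30 = day 245, or 215 + 100 = day 315.
- With 49 days of radiotherapy and the 4-week delay to maintenance allowed in Protocol Section 4.5.2.2: 49 + 28 + 28 + 140 + 5 = day 250. Coverage ends at day 280, or day 350. Delays to later cycles, or extra cycles in Japan, would extend this further.
- Nivolumab coverage can run to the data cut, 23 to 33 months after randomization (SAP Section 5: 10 months of accrual plus 23 of follow-up).

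**Assumptions, not in the documents**
- Time to stopping S is exponential with median 4, 6 or 10 months, is the same in both arms, and is capped at 28 months (the middle of 23 to 33).
- The AE hazard is identical in both arms. It is constant, or front-loaded (0.8 per year to day 70, then 0.2), or late (0.2, then 0.8). Day 70 = 42 + 28 is the end of radiotherapy and the break.
- The window is min(S, 215) + tail for temozolomide and S + tail for nivolumab.

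**Worked case: median 6 months (182.6 days), 30-day tail**
- Mean of the uncapped S is 182.6 / ln 2 = 263.5 days.
- Mean temozolomide window: 263.5 × (1 − 2^(−215/182.6)) + 30 = 147.0 + 30 = 177.0 days (5.8 months).
- Mean nivolumab window: 263.5 × (1 − 2^(−28/6)) + 30 = 253.1 + 30 = 283.1 days (9.3 months). The ratio is 1.60.
- Mean time before day 70, both arms: 30 + 263.5 × (1 − 2^(−40/182.6)) = 67.1 days.
- Front-loaded rate, temozolomide: (0.8 × 67.1 + 0.2 × 109.9) / 177.0 = 0.428 per year. Nivolumab: (0.8 × 67.1 + 0.2 × 216.0) / 283.1 = 0.342. The ratio is 0.80.
- Late rate, temozolomide: (0.2 × 67.1 + 0.8 × 109.9) / 177.0 = 0.572 per year. Nivolumab: (0.2 × 67.1 + 0.8 × 216.0) / 283.1 = 0.658. The ratio is 1.15.
- With a constant hazard the rate is that constant in both arms, so the ratio is 1.00.

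Crude incidence is the mean of 1 − exp(−cumulative hazard) over each arm's windows, here from 400,000 simulated stop times. For the 6-month median it is 18.6% vs 22.7% front-loaded and 23.3% vs 33.6% late (temozolomide vs nivolumab).

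**Ratios, nivolumab to temozolomide (true value 1.0), 30-day tail**

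| Median stop (months) | Mean window (months), temozolomide / nivolumab | Crude, front-loaded | Crude, late | Rate, constant | Rate, front-loaded | Rate, late |
|---|---|---|---|---|---|---|
| 4 | 5.1 / 6.7 | 1.11 | 1.27 | 1.00 | 0.86 | 1.12 |
| 6 | 5.8 / 9.3 | 1.22 | 1.44 | 1.00 | 0.80 | 1.15 |
| 10 | 6.6 / 13.3 | 1.39 | 1.69 | 1.00 | 0.74 | 1.17 |

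The 100-day tail moves the ratios nearer to 1. The lowest crude ratio is 1.09. The rate ratios are 0.91, 0.86 and 0.81 front-loaded, and as low as 1.06 late.

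**Second check**

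This followed each arm's dosing calendar, with median PFS of 4 to 12 months and different hazards (front-loaded 3.0 then 0.5 per year; late 0.5 then 1.5, changing at day 112). Rate ratios were 0.66 to 0.90 front-loaded, 1.09 to 1.28 late and 1.00 constant. With a constant hazard of 1.0 per year, crude incidence was 36.3% vs 44.9% at a 6-month median. The crude excess shrinks for common, early events: 47.4% vs 49.0% (ratio 1.03) for the front-loaded hazard at a 4-month median with the 30-day tail.

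**Effect of a common cut**

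Cutting both arms at day 245 (day 315 with the 100-day tail) returns both ratios to 1.00 in the simple model. In the dosing-calendar model, rate ratios become 0.99 to 1.00 and incidences agree within 0.7 percentage points.

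**The case against.** The strongest reply is that the tables describe each regimen as given. Treatment to progression is part of the nivolumab regimen, and a fixed post-dose tail is an ordinary convention. The readable SAP also has relevant displays: person-year rates, a Kaplan-Meier curve of treatment duration by arm (Section 7.4.1), time to onset for select AEs (Section 7.1.1.1) and a drug-related AE definition (Section 7.1.1). Section 7.1.1 sets defaults only and refers to Section 7.6.9 for the repeated-event analysis. Section 7.6 is almost wholly redacted.

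Much of this stands. The planned tables are legitimate and should stay, and nobody can say from the public text that a time-restricted analysis is absent. But the duration curve shows the imbalance without adjusting for it, and time to onset covers select AEs only.

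Three stronger readings are tempting, and the documents do not support them:
- A reader might infer that the control window is fixed. It is capped. It also ends early at progression or toxicity, and it can run past day 245.
- A reader might infer that person-year rates also differ by construction. They do not: under a constant hazard they are equal.
- A reader might infer that the rate must understate nivolumab toxicity because radiotherapy comes early. That holds only if toxicity is front-loaded. If disease, steroid or late-radiation events dominate, the hazard rises and the rate overstates it.

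**Conclusion.** The concern holds in a limited form. On the readable text, crude side-by-side AE percentages cover unequal time and would favor temozolomide even with identical toxicity, by a ratio of about 1.1 to 1.7 under the main assumptions. The overall person-year rate is a safe correction only if the hazard is roughly constant. Otherwise it can err either way (0.74 to 0.91 front-loaded, 1.06 to 1.17 late), and the documents do not show which applies. Only the window arithmetic comes from the documents. The ratios rest on the assumed stop times and hazards, and they shift with other choices, as the second check shows. This is an inexpensive improvement to the safety reporting, conditional on what Section 7.6 contains.

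**What to change.** In SAP Section 7.1.1, unless Section 7.6 already does so (in which case a cross-reference is enough), keep the planned tables and add:

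- (a) Rates per 100 person-years by period since first dose, with the same cut points in both arms: day 1-70, day 71-245 and after day 245.
- (b) A side-by-side incidence table of on-treatment events up to a common day, 245 for the 30-day window and 315 for the 100-day window. Show later events separately for both arms, because control subjects with delays, 49 days of radiotherapy or extra cycles can also have them.

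This removes the difference caused by the dosing schedules. It does not remove differences caused by earlier progression or toxicity in one arm. The cost is longer safety tables and some extra programming on data already collected. No dosing or clinical rule changes.

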7.1.1.1 Select Adverse Events

The select Adverse Events (select AEs) consist of a list of preferred terms grouped by specific category (e.g. pulmonary events, gastrointestinal events categories, etc.). AEs that may differ from or be more severe than AEs caused by non-immunotherapies and AEs whose early recognition and management may mitigate severe toxicity are included as select AEs. Categories of select AEs may include subcategories (e.g. adrenal disorders, diabetes, pituitary disorders, and thyroid disorders are subcategories of the endocrine event category).

The list of MedDRA preferred terms used to identify select adverse events is revisited quarterly and updated accordingly. The preferred terms used for the selection at the time of the database lock will be provided by categories/sub-categories.

In addition to the frequency and worst severity of select AEs, time-to onset, time-to resolution, and time-to resolution where immune modulating medication was initiated will be analyzed for each specific category/subcategory when applicable.

Further details on the definitions of select adverse event, time-to onset and time-to resolution are described in [APPENDIX 1](#).

